#### 12.4 Monitoring Guidelines

Monitoring guidelines will be in place to monitor events separately for each component separately. Stopping guidelines will be enacted using a continuous monitoring strategy based on an adaptation of Pocock stopping boundaries. (Ivanova 2005) In the event that the stopping rule is triggered, enrollment will be halted. The event will be reviewed by the study team with follow-up reporting of the findings to the FDA and IRB before enrollment is restarted.

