#### 5.2 Patient Enrollment to Study Treatment in OnCore

To be eligible for study treatment, the patient must sign the treatment consent and meet each inclusion criteria and none of the exclusion criteria on the eligibility checklist based on an eligibility assessment documented in the patient's medical record.

After transplant, the study doctor will need to assess the patient to determine if the criteria in Section 4.3 is met and continuing on the study is in the best interest of the patient based on their current medical situation.

The patient is assigned to the currently enrolling treatment plan after the transplant and confirmation of continuing eligibility.

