#### 5.3 Patients Who Do Not Begin Study Treatment

If a patient is enrolled in the study (i.e. assigned a sequence number) and is later found unable to begin FT596, the patient will be removed from study and treated at the physician's discretion. The study staff will update OnCore of the patient's non-treatment status (off study) with the reason for removal from study prior to starting study treatment clearly indicated. The patient will be replaced to complete enrollment. Any data and research samples collected up to this point will be retained as detailed in the written consent document.

If a patient receives FT596, they are considered on treatment and most continue follow-up per Section 8.

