#### 6 Treatment Plan

Primary supportive care is to continue according to the primary transplant protocol. In order to provide optimal patient care and to account for individual medical conditions, investigator discretion may be used in the prescribing of all supportive care drug therapy (i.e. acetaminophen, diphenhydramine, antimicrobials, etc.).

Because they may inhibit NK cell function, systemic corticosteroids should be avoided during the treatment period (3 days before and through 14 days after FT596) unless absolutely required. Intravenous glucocorticoid as premedication for rituximab may be administered per the USPI or institutional guidelines. Methylprednisolone should be used as preferred glucocorticoid premedication given its shorter half-life.

Treatment may be given as an inpatient or an outpatient. There is no protocol driven requirement for hospitalization.

For scheduling purposes, the rituximab/FT596 "package" is administered with a +3 day window from the targeted FT596 administration day (Day 30 or Day 7). Rituximab or an FDA approved biosimilar is given 2-3 days (48 to 72 hours) prior to the planned FT596 infusion.

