#### 6.2 Component 1: Identify FT596 MTD When Given on Day 30 Only

In Component 1, all patients will receive a single dose of FT596 on Day 30 (+3 days) post-transplant. Rituximab (Rituxan or an FDA approved biosimilar, e.g. Truxima and Ruxience) 375 mg/m^2 is administered 2-3 days prior to FT596.

Up to three FT596 dose levels are planned: Dose Level 1:  $9x10^7$  cells/dose, Dose Level 2:  $3x10^8$  cells/dose, Dose Level 3:  $9x10^8$  cells/dose with a Dose Level -1:  $3x10^7$  cells/dose tested only if DLT at DL1. Refer to Section 3 regarding the required staggering of enrollment.

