### 8.1 Required Clinical Care Evaluations

	Screening prior to	Post-Transplant Confirmation of	Day of FT596	Post FT596 Infusion (using Day 0 as the day of infusion)				Abstract from patient's EMR at	3, 6, and 12 months from		
	Transplant	Continuing Eligibility (approximately Day 21 for Component 1)	approved biosimilar, e.g. Truxima and Ruxience) Infusion (-3 day window for labs and assessment)	Infusion (Day 0^)	day 2	day 7	day 14	day 21	EOT visit day 28	each SOC visit until the 3 month post-transplant	transplant at the time of SOC visit
Consent	X 		-								
Screening Assessment	Х										
Brief Medical Assessment				Х	Х	Х	Х	Х	Х		
Medical History	Х	Х									Х
Concomitant Medications	Х			Х							
Assess Venous Access		Х									
Physical Exam	Х	Х	Х								Х
ICANS (neurotoxicity) monitoring – refer to Section 7.4		X		Х		X 	X 	X 	X 		X
Weight	Х	Х	X								
Height	Х										
Vitals and Pulse Oximetry	Х	Х	X	Х					X 		
Toxicity Assessment	Х	Х	Х	Х	Х	Х	Х	Х	Х	Х	Х
CBC, diff, plt	Х	Х	X	Х	Х	Х	Х	Х	Х	Х	Х
Basic metabolic panel (BMP) 				Х	Х	Х	Х	Х			Х
Comprehensive metabolic panel (CMP) or equivalent  plus magnesium, phosporus	X	X	X						X	X	
eGFR	Х	Х									
Urine or serum pregnancy test for WOCBP 	х	X									
If pt develops cytokine release syndrome (CRS): CRP, ferritin and, if testing available, IL-6				If CRS is s At diagnos outpt visit t	uspecter is docun until reso	d obtain nent CR plution of	CRP, ferr P, ferritin a CRS. Re	itin and IL- and IL-6 lev fer to Secti	6 levels vels 3 x week on 7.3.	ly if inpt or at every	
If pt develops neurotoxicity				Refer to Se	Section 7.4 for FDA recommended testing 						

	Screening prior to	Post-Transplant Confirmation of	Day of Rituximab Day of Rituxan or an EDA ET59		Day of Post FT596 Infusion (using Day 0 as the day of infusion)			Abstract from patient's EMR at	3, 6, and 12 months from		
	Transplant	Continuing Eligibility (approximately Day 21 for Component 1)	approved Infusion biosimilar, e.g. (Day 0^) Truxima and Ruxience) Infusion (-3 day window for labs and assessment)	day 2	day 7	day 14	day 21	EOT visit day 28	each SOC visit until the 3 month post-transplant	transplant at the time of SOC visit	
Disease staging	Х	Х									Per SOC
CXR or chest CT scan	X										
PFTs⁵	Х										
EKG	Х										

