# The rules are based on the time from transplant and occurring after the FT596 infusion.

#### 12.4.1 Mortality by Day 100

Enrollment will be halted and reviewed by the study team with follow-up notification to the FDA and IRB of the findings before enrollment is restarted.

#### 12.4.2 Grade III-IV Acute GVHD by Day 100

Enrollment will be halted and reviewed by the study team with follow-up notification to the FDA and IRB of the findings before enrollment is restarted.

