#### 12.4.4 Any Two Grade 4 Dose Limiting Toxicities (DLTs)

If two Grade 4 DLTs occur, enrollment will be halted and reviewed by the study team with follow-up notification to the FDA and IRB of the findings before enrollment is restarted.

#### 12.4.5 Grade 4 Lymphopenia (<200 cells/uL) at Day 100

The goal is to construct a boundary based on lymphopenia such that the probability of early stopping is at most 10% if the rate is equal to 20% and our sample size is at most 18. With these stipulations, the trial will be stopped and reviewed if 3/4, 4/7, 5/10, 6/13 or 7/17 patients at any time have Grade 4 related lymphopenia at Day 100.

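### The stopping rules in 12.4 halt enrollment only; nothing requires rituximab or FT596 to be held in a Component 1 patient already assigned but not yet infused

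*Combined protocol and SAP*

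**What the plan says.** The lead paragraph of 12.4 states: "In the event that the stopping rule is triggered, enrollment will be halted". Enrollment restarts after the study team has reviewed the event and reported its findings to the FDA and IRB. Rules 12.4.1 and 12.4.2 use the same action, "Enrollment will be halted and reviewed by the study team", and 12.4.4 reads "If two Grade 4 DLTs occur, enrollment will be halted and reviewed by the study team". None of them mentions rituximab, FT596 or patients already in line for treatment.

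The steps from assignment to infusion are set out elsewhere:

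- Section 5.2: "The patient is assigned to the currently enrolling treatment plan after the transplant and confirmation of continuing eligibility".
- Section 8.1: the column for that confirmation is headed, in part, "Continuing Eligibility (approximately Day 21 for Component 1".
- Section 6: "Rituximab or an FDA approved biosimilar is given 2-3 days (48 to 72 hours) prior to the planned FT596 infusion".
- Section 6.2: "In Component 1, all patients will receive a single dose of FT596 on Day 30 (+3 days) post-transplant".
- Section 5.3 deals with someone who is enrolled but undosed: "If a patient is enrolled in the study (i.e. assigned a sequence number) and is later found unable to begin FT596". Such a patient is removed and replaced.

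**The concern.** Section 5.3 treats a patient as enrolled once a sequence number is given, before any FT596. A halt on enrollment therefore does not, by its words, reach a patient who already has a number and is waiting for rituximab or FT596. Section 7 says there are no clinical data on FT596, so these halts are a main protection for the next patient. After a death, severe GVHD or a second Grade 4 DLT, new entries stop. Whether the patient already in line receives the product under review is left to each site to infer.

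**Working it through.** **Is there a hold elsewhere?** The sections that delay or withhold FT596 all turn on the patient's own condition:

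- 4.3: post-transplant criteria, with up to 3 days' delay.
- 5.2: the study doctor's judgment of that patient's best interest.
- 6.1.2 and 6.6: that patient's rituximab toxicity, with up to 7 days' delay.
- 6.1.2 and 7.1: that patient's own infusion reaction.

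None refers to a stopping event in someone else. Rule 12.4.5 (lymphopenia) says the trial, rather than enrollment, is stopped, but names no dosing hold. It holds the only numeric boundary in 12.4. An exact patient-by-patient binomial calculation gives an 8.1% chance of early stopping at a 20% rate with 18 patients, within the stated 10%. That boundary is sound and is not at issue.

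**Inputs.** Assignment is at about Day 21 (8.1) or, as a lower limit that I assume, as late as rituximab, 2 to 3 days before FT596 (6). Infusion is on Day 30 to 33 (6.2). The Day 100 clock starts at transplant (12.4). Spacing is 28 days between patients at Dose Level 1, and 28 then 14 days in later cohorts; the next cohort is assigned once the third patient has reached 28 days (12.1). Accrual is 12 to 18 per year (12.2). Six per year is my assumption for slow accrual.

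**Assigned-but-undosed lag, L.** 30 − 21 = 9 days to 33 − 21 = 12 days; lower limit 2 to 3 days.

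**Day 100 monitoring after infusion, M.** 100 − 30 = 70 days; 100 − 33 = 67 days. After a 28-day separation, 70 − 28 = 42 or 67 − 28 = 39 days remain. After a 14-day separation, 56 or 53 remain. The stagger does not close the gap.

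**Later patients, k, who wait during one patient's monitoring.** At 12 per year the gap is 365/12 = 30.4 days. Infusions at 30.4 and 60.8 days fall inside 67 to 70, and the next, at about 91, is assigned no earlier than 91 − 12 = 79; so k = 2. Minimum spacing also gives k = 2 (for example, infusions at 0, 28 and 56 days in the first cohort). Eighteen per year (365/18 = 20.3 days) is faster than the later-cohort minimum average of (28 + 14 + 28)/3 = 23.3 days, so minimum spacing governs. At 6 per year the gap is 60.8 days and k = 1.

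**Share of monitoring time = k × L / M.**

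| Spacing | k | Assigned at Day 21 | Assigned at rituximab |
|---|---|---|---|
| Minimum, or 12 per year | 2 | 18/70 = 26% to 24/67 = 36% | 4/70 = 6% to 6/67 = 9% |
| 6 per year (assumed) | 1 | 9/70 = 13% to 12/67 = 18% | 2/70 = 3% to 3/67 = 4% |

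**Overlap with the 28-day DLT window (12.4.4).** This depends on what the stagger separates.

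- *Infusion to infusion.* With a 28-day gap the next patient is assigned 28 − 12 = 16 to 28 − 9 = 19 days after the previous infusion. With a 14-day gap, assignment is at 2 to 5 days. Either way 9 to 12 days overlap (2 to 3 at the lower limit).
- *Next patient enrolled only after the previous 28-day assessment.* Overlap is 0 at Dose Level 1 and between patients 1 and 2 of later cohorts. Between patients 2 and 3, assignment at 14 days leads to infusion at 14 + 9 = 23 to 14 + 12 = 26 days, still inside 28, so the overlap remains there.
- *Between cohorts.* Overlap is 0 on either reading, because assignment waits for the third patient's 28 days. Only the Day 100 rules are then open, with 39 to 42 days left.

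**The case against.** The strongest reply is that enrollment in this protocol means entry to treatment. Section 5.2 is titled as enrollment to study treatment, 6.2 and 6.3 call the patient spacing a stagger of enrollment although it exists to observe toxicity after infusion, and 12.4.5 speaks of stopping the trial. A careful investigator would probably pause. Stopping events reach the lead center within 24 hours (table in 10.5 and 10.6), and 5.3 allows removal of a patient unable to begin FT596 without limiting the cause. All this shows that a hold is possible and workable. It does not make one required, and 5.3 uses enrolled for a patient who has not started FT596. The routine site calls in 11.5 are two weeks apart, longer than a 9 to 12 day lag.

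The size is also uncertain. Day 21 is only approximate, 5.2 names no day, and labs and examination are repeated around rituximab. The upper figures need assignment at Day 21. That stands, which is why both bands are shown.

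The 12.4.4 part is small if toxicity is as expected. With 3, 3 and 6 patients at DLT rates of 1%, 3% and 6% (12.1, 12.2), the chance of no DLT is 0.99³ × 0.97³ × 0.94⁶ = 0.611. The chance of exactly one is 0.611 × (0.03/0.99 + 0.09/0.97 + 0.36/0.94) = 0.309. Two or more therefore has probability of about 8%, counting DLTs of any grade; two Grade 4 DLTs are rarer. That stands too, and puts the weight on the Day 100 rules.

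Finally, an automatic hold can cost a high-risk patient the dose. That is a fair reason to choose case-by-case review, but the protocol should then say so.

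**Conclusion.** The gap is real and modest. After a trigger under 12.4.1, 12.4.2 or 12.4.4, the required action stops short of the Component 1 patient already assigned and not yet infused, usually one patient per halt. For the Day 100 rules, such a patient exists for about 3% to 9% of a treated patient's monitoring time with late assignment, and about 13% to 36% with assignment at Day 21. The figures assume regular or minimum spacing, and the lower end of each band assumes 6 patients per year.

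Three stronger readings are not supported:

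- *That the protocol tells sites to dose after a trigger.* Section 6.2 describes the treatment plan in general terms, and 12.4 is silent about the waiting patient; it neither directs dosing nor prevents a hold.
- *That the percentages are chances of a trigger or of harm.* They are shares of time; the documents give no rate for deaths or GVHD after FT596.
- *That 12.4.4 is exposed throughout.* There is no DLT-window overlap between cohorts, and within a cohort it depends on how the stagger is read.

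**What to change.** Add to the lead paragraph of 12.4, so that it governs every rule and both components:

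> When a stopping rule is met, enrollment and all rituximab and FT596 not yet given in the affected component are suspended until the study team has reviewed the event and reported its findings to the FDA and IRB. The hold includes any patient who has received rituximab but not FT596. A patient whose dosing window passes during the hold is replaced under Section 5.3.

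The release point is deliberately the one that 12.4 already sets for restarting enrollment. Rituximab recipients need naming because the 7-day limit in 6.6 concerns rituximab toxicity only. It would also help to state in 5.2 the day on which assignment takes effect, and in 12.1 whether the stagger runs from infusion to infusion.

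The drafting cost is a few sentences. The clinical cost is that the dosing window is only +3 days, so usually one waiting patient per halt may lose the dose. That includes halts where the death proves to be from lymphoma, since 12.4.1 counts any death after FT596 by Day 100. Each replacement also adds some accrual time.

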# The rules are based on the time from transplant and occurring after the FT596 infusion.

#### 12.4.1 Mortality by Day 100

Enrollment will be halted and reviewed by the study team with follow-up notification to the FDA and IRB of the findings before enrollment is restarted.

#### 12.4.2 Grade III-IV Acute GVHD by Day 100

Enrollment will be halted and reviewed by the study team with follow-up notification to the FDA and IRB of the findings before enrollment is restarted.

#### 12.4.3 Any Grade 4 FT596 Infusion Related Reaction

Enrollment will be halted and reviewed by the study team with follow-up notification to the FDA and IRB of the findings before enrollment is restarted.

#### 12.4.4 Any Two Grade 4 Dose Limiting Toxicities (DLTs)

If two Grade 4 DLTs occur, enrollment will be halted and reviewed by the study team with follow-up notification to the FDA and IRB of the findings before enrollment is restarted.

#### 12.4.5 Grade 4 Lymphopenia (<200 cells/uL) at Day 100

The goal is to construct a boundary based on lymphopenia such that the probability of early stopping is at most 10% if the rate is equal to 20% and our sample size is at most 18. With these stipulations, the trial will be stopped and reviewed if 3/4, 4/7, 5/10, 6/13 or 7/17 patients at any time have Grade 4 related lymphopenia at Day 100.

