	
 
Monitoring guidelines for excessive toxicity (Stopping Rule events) Component 1 and Component 2 (ONLY POST FT596 EVENTS COUNT HERE))
 
The following events occurring after the FT596 infusion are measures of excessive toxicity based on Day 0 as the Transplant Day). Each component is monitored separately.
 
Mortality by Day 100
 
Grade III-IV Acute GVHD by Day 100
 
Any Grade 4 FT596 Infusion Related Reaction
 
Any Grade 4 Dose Limiting Toxicity (DLT) event
 
Grade 4 Lymphopenia (<200 cells/uL) at Day 100
 
Engraftment failure by Day 28 (Component 2 only)
 

Study Products:	FT596 and rituximab (Rituxan or any FDA approved biosimilar)
Primary Objective:	The primary objective of this study is: Component 1: Establish a maximum tolerated dose (MTD) of FT596 when given 30 days after transplant. Component 2: Confirm the MTD and the safety of giving a single dose of FT596 at Day 7 post-transplant using one dose level below the MTD (MTD -1) or the MTD from Component 1.

Secondary Objectives:	
 
To evaluate the adverse events related to FT596 administered post auto-HSCT in combination with rituximab (Rituxan or an FDA approved biosimilar, e.g. Truxima and Ruxience).
 
To determine preliminary efficacy based on progression free survival (PFS) and relapse/progression at 12 months post auto-HSCT.
 
To determine the incidence of non-relapse mortality at 100 days and 1 year post auto-HSCT.
 

Objectives:	
 
To evaluate persistence of FT596 in blood after each FT596 infusion by immunophenotyping and PCR up to 1 year.
 
To assess the association of FT596 cell persistence with safety and anti-tumor activity.
 
To assess the association of baseline clinical and tumor characteristics with safety and response endpoints following administration of FT596.
 

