Up to three FT596 dose levels are planned for administration on Day 30: Dose Level 1: 9x10^7 cells/dose, Dose Level 2: 3x10^8 cells/dose, Dose Level 3: 9x10^8 cells/dose with a Dose Level -1: 3x10^7 cells/dose tested only if DLT at DL1.The maximum tolerated dose will be determined by using a modified continual reassessment method (CRM).

Patients are enrolled in cohorts of 3 starting at Dose Level 1. A minimum of 28 days will separate each cohort. For Dose Level 1 a minimum of 28 days will separate each patient to assess for dose limiting toxicity (DLT). In subsequent cohorts, the 1st and 2nd patient will be separated by at least 28 days and at least 14 days will separate the 2nd and 3rd patient.

Each new cohort of three patients will be sequentially assigned to the most appropriate dose based on the updated toxicity probabilities under the continuous reassessment method (CRM), and the MTD will be identified when the total sample size of 18 is exhausted or 6 patients are sequentially enrolled at the same dose.

Definitions of dose limiting toxicity and monitoring for excessive toxicity are found in Section 12.4.

Component 2: To determine the safety of FT596 when given at Day 7 based on the MTD from Component 1.

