#### 10.4 Dose Limiting Toxicity and Excessive Toxicity (Stopping Rule Events) Documentation and Reporting Requirements

All patients enrolled in Components 1 and 2 are monitored for dose limiting toxicity (DLT) and excessive toxicity (early stopping events) specific to the Component. Refer to Section 12 for definitions. (ONLY POST FT596 EVENTS COUNT)

In addition to documenting the event in the study's CRF's, all DLT and SR events are to be documented on the Event Form found in OnCore per Masonic Cancer Center procedures.

An event that counts as a DLT does not necessarily constitute a SAE and should be reported as such only if they meet the criteria for reporting as defined in Section 10.5.

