#### **12 Statistical Considerations**

#### 12.1 Study Designs

This study consists of two components. The 1st component is a Phase I clinical trial to identify the maximum tolerated dose (MTD) of FT596 at Day 30 post FT596 infusion. The second component is a Phase I clinical trial to identify the MTD of FT596 at Day 7 post FT596 infusion. Rituximab is given 2-3 days before FT596. In addition to identifying the MTD and providing preliminary estimates of safety, secondary objectives include providing preliminary descriptive estimates of efficacy such as progression-free survival, relapse and non-relapse mortality along with their error measurements. Correlative objectives include measurement of the persistence of FT596 in blood after each FT596 infusion by immunophenotyping and PCR up to 1 year, the association of FT596 persistence with safety and anti-tumor activity.

Component 1 will identify the MTD of FT596 when given as a single dose at Day 30. Up to three FT596 dose levels are planned (Dose Level 1:  $9x10^7$  cells/dose, Dose Level 2:  $3x10^8$  cells/dose, Dose Level 3:  $9x10^8$  cells/dose with a Dose Level - 1:  $3x10^7$  cells/dose tested only if DLT at DL1).

**Component 1 dose limiting toxicity** is defined as any of the following events within 28 days after the FT596 dosing based on CTCAE v5:

- Grade 4 hematologic toxicity lasting > 7 days (not including lymphopenia)
- Grade 4 non-hematologic toxicity
- Grade ≥3 FT596 Infusion Related Reaction
- Grade 2 acute GVHD that requires steroid therapy >7 days or progression after 3 days of steroids or has partial response after 14 days of treatment
- Grade ≥3 acute GVHD
- Grade 4 cytokine release syndrome (CRS)
- Grade 3 CRS that does not resolve to < Grade 2 in 72 hours
- Grade 3 neurotoxicity

- Grade 3 organ toxicity involving vital organs; cardiac, central nervous system and pulmonary that lasts for longer than 7 days including Grade 3 Investigations (laboratory values) of any duration that indicate damage to vital organs.
- Any Grade 3 non-hematological toxicity that does not resolve to ≤Grade 2 within 72 hours; excepting Grade 3 renal and hepatic toxicity which may take up to 7 days to resolve to ≤Grade 2

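### The synopsis, both schemas and Section 6.4 list any Grade 4 DLT as a stopping event with no count, while Section 12.4.4 pauses enrollment only at the second

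*Combined protocol and SAP*

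**What the plan says.** Four places list Grade 4 DLTs among the events of excessive toxicity, in the same words and with no number: the synopsis (monitoring guidelines), the Component 1 schema, the Component 2 schema and Section 6.4. Each has "Any Grade 4 Dose Limiting Toxicity (DLT) event".

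Section 12.4.4, whose heading specifies two events, sets the rule: "If two Grade 4 DLTs occur, enrollment will be halted and reviewed by the study team", with notification of the FDA and IRB before enrollment restarts. Section 12.4 gives the general consequence: "In the event that the stopping rule is triggered, enrollment will be halted".

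Some text directs the reader to the statistical section. Section 6.4 cites Section 12.4. Section 3 says that "Definitions of dose limiting toxicity and monitoring for excessive toxicity are found in" Section 12.4. Section 10.4 says that patients are "monitored for dose limiting toxicity (DLT) and excessive toxicity (early stopping events) specific to the Component" and refers to Section 12. The synopsis and schema lists carry no such reference.

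**The concern.** The word at the head of the list item naturally reads as one event. The item beside it has the same form, "Any Grade 4 FT596 Infusion Related Reaction", and Section 12.4.3 halts enrollment on it with no count above one. A reader who applies that pattern to the DLT item concludes that one Grade 4 DLT pauses enrollment. A reader of Section 12.4.4 concludes that it takes two.

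The difference matters for a single Grade 4 DLT that no other rule in Section 12.4 covers. Under the DLT definition in Section 12.1, examples are Grade 4 cytokine release syndrome and Grade 4 hematologic toxicity persisting beyond 7 days. On the first such event, a site using the schema and a study team using Section 12.4.4 could disagree on whether enrollment pauses and whether the review with FDA and IRB notification starts. Reporting is affected too. The event table in Sections 10.5 and 10.6 gives stopping-rule events their own form with a 24-hour deadline, and the Component 1 summary for the FDA includes them. Section 7 states that there are no clinical data on FT596, so the threshold should be the same wherever it appears.

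**Working it through.** **Step 1. The listed items against their rules in Section 12.4.**

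| Item | Synopsis, schemas, Section 6.4 | Section 12.4 |
|---|---|---|
| Mortality by Day 100 | no count | 12.4.1: no count |
| Grade III-IV acute GVHD by Day 100 | no count | 12.4.2: no count |
| Grade 4 infusion reaction | any, no count | 12.4.3: any, no count |
| Grade 4 DLT | any, no count | 12.4.4: two, in heading and text |
| Grade 4 lymphopenia at Day 100 | no count | 12.4.5: boundary from 3/4 to 7/17 |
| Engraftment failure by Day 28 (Component 2) | no count | 12.4.6: no count |

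The DLT item is the only one whose label differs in count from its Section 12.4 heading. Lymphopenia also has a multi-patient threshold, but its label does not change and does not begin with the word that suggests a single event.

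**Step 2. How often the two readings would differ.** The plan gives no operating characteristics for this rule and no Grade 4 DLT rate, so there is no figure to reproduce. The following is an illustration.

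Inputs:
- Component 1: prior DLT probabilities of 1%, 3% and 6% (Section 12.1), with 3, 3 and 6 patients (Section 12.2, Table 1, expected scenario).
- Component 2: tentative priors of 5% and 10% for Dose Levels 2 and 3 (Section 12.1), with 6 and 6 patients (Table 2, expected scenario).
- Twelve patients per component, the most likely number in Section 12.2.
- Assumptions: independent patients, fixed allocation, at most one event per patient.

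Formulas, with n_i patients at rate p_i:
- P(0) = Π(1 − p_i)^n_i
- P(1) = P(0) × Σ n_i p_i/(1 − p_i)
- One-event reading: 1 − P(0). Two-event reading: 1 − P(0) − P(1). The gap is P(1).

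Every DLT taken as Grade 4:
- Component 1: P(0) = 0.99³ × 0.97³ × 0.94⁶ = 0.6109. P(1) = 0.6109 × (0.0303 + 0.0928 + 0.3830) = 0.3092. Chance of a pause: 38.9% against 8.0%.
- Component 2: P(0) = 0.95⁶ × 0.90⁶ = 0.3907. P(1) = 0.3907 × (0.3158 + 0.6667) = 0.3838. Chance of a pause: 60.9% against 22.6%.

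Varying the share of DLTs that are Grade 4 (assumed):

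| Share Grade 4 | Component 1: one / two / gap | Component 2: one / two / gap |
|---|---|---|
| All | 38.9% / 8.0% / 30.9 points | 60.9% / 22.6% / 38.4 points |
| Half | 21.6% / 2.3% / 19.3 points | 36.9% / 7.2% / 29.7 points |
| Quarter | 11.4% / 0.6% / 10.8 points | 20.3% / 2.0% / 18.3 points |

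**Step 3. Limits of these figures.** At the plan's priors they overstate the gap. Those priors include Grade 4 infusion reactions, Grade IV GVHD and, in Component 2, non-engraftment. Sections 12.4.2, 12.4.3 and 12.4.6 attach no count to these events, so on their natural reading they pause enrollment at the first event either way. The figures also depend on the priors. At 1.5 times the Component 1 priors (1.5%, 4.5%, 9%), with every DLT Grade 4, P(1) = 0.4727 × 0.7805, or about 37%, which exceeds the 30.9% above.

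**The case against.** The strongest reply is that Section 12.4 is the operative text and is clear. It alone says what happens when an event occurs, and Section 12.4.4 gives the count in both heading and body. The lists contain no instruction to halt, and several sections refer to Section 12.4 or Section 12. The lists also show lymphopenia without a count, although Section 12.4.5 says "the trial will be stopped and reviewed if 3/4, 4/7, 5/10, 6/13 or 7/17 patients" reach the boundary. Anyone treating each listed item as a one-event trigger would misread that one too. The lists also have a sensible reporting role, since a two-event rule works only if each Grade 4 DLT is reported.

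The practical exposure is narrowed as well. Serious events are reportable within 24 hours, and unexpected life-threatening suspected reactions go to the FDA within 7 days. First-cohort patients are separated by 28 days, later cohorts wait for the previous cohort's third patient to reach 28 days, and the FDA reviews Component 1 before Component 2 opens.

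Most of this stands. It makes the problem an ambiguity of wording rather than a flaw in the design, and the probabilities are illustrative and should not carry the point. It does not remove the point. No text says that the lists name event types only or that Section 12.4 prevails. The synopsis and schemas, which sites are likely to consult, have no cross-reference. None of the other safeguards settles whether a first event pauses enrollment.

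**Conclusion.** The concern holds. A safety threshold is worded one way in four places and another way in Section 12.4.4, and a reader could reasonably take a first Grade 4 DLT as a trigger. It should be fixed.

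The practical gap is confined to a first Grade 4 DLT that no other Section 12.4 rule covers. What turns on it is an enrollment pause pending review, not closure of the trial; CRM updating, staggering and the other monitoring rules continue to apply. At the plan's priors, the two readings differ by at most about 31 percentage points in Component 1 and 38 in Component 2. If only a quarter of DLTs are Grade 4, the differences are about 11 and 18 points, before allowing for events that pause enrollment on either reading. The sizes rest on assumed Grade 4 shares, a fixed allocation and, for Component 2, a skeleton that the plan offers only as a possibility. The inconsistency in the text rests on none of these.

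**What to change.** Reconcile the synopsis, the Component 1 schema, the Component 2 schema, Section 6.4 and Section 12.4.4 so that all five state the same number of Grade 4 DLTs that halts enrollment. Alternatively, add to each list an explicit statement that it names event types and that Section 12.4 sets the count for each. The sponsor decides the number.

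In the same edit, state in Section 12.4.4 whether a Grade 4 infusion reaction or Grade IV GVHD, each with its own rule, also counts toward that number, and whether the events must occur in different patients. Neither is stated now.

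The cost is protocol wording only. Sample size and CRM model are untouched.
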